The e-CBT-I will be delivered by a mobile application (eSleep) which contains a digital, self-paced, and highly interactive programme. The Chinese version (simplified Chinese/Mandarin) of the application has been designed to adapt for the language background of the participants in China. The program is developed as based on wellestablished CBT-I treatment protocol and consists of six 20-30 minutes sequential modules unlocked weekly with animated elements, including an overview of sleep, sleep restriction, stimulus control, cognitive therapy, structured worry time and relapse prevention. During sleep restriction module (session 2), participants will obtain a "sleep prescription" from the application, specifying their sleep window (from initial bedtime to final arising time) for the next seven days. The setting of the sleep window is based on individual's average total sleep time from the previous week, while adhering to the 5hour minimum rule. The sleep prescription is adjusted weekly based on the following criteria: 1) if sleep efficiency > 85%, increase sleep window by 15-20 min; 2) if sleep efficiency < 80%, decrease sleep window by 15-20 min; and 3) if sleep efficiency is between 80%-85%, keep sleep window the same. The application control management system provides online analytics, which allows the researchers to monitor individual's participation during the intervention by assessing how many sessions were completed and the number of weeks to complete the course. Participants will have access to the e-CBT-I treatment for 12 weeks, allowing them additional time to complete the intervention in case they were unable to completed it within the initial 6-week period. Individualized text messages will be sent to the participants regularly, asking them to complete the treatment sessions and sleep diaries on time. The participants will also be contacted weekly to prevent possible dropout from occurring during the intervention. The PI and collaborators have had the research and clinical experiences in delivering CBT-I, and the e-CBT-I treatment protocol has been tested and modified from our previous studies [Trial registration: clinicaltrials.gov Identifier: NCT03438331; funded by Early Career Scheme, Ref. 27613017] 59.

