The HE, a psychoeducation/information-approach, delivered in control group has been adopted in the previous study ⁵⁰. It also consists of six consecutive sessions which contains information about general sleep knowledge, functions of human organs, nutrition, environmental health, brain health, identification and treatments of common diseases, but the contents are not related to any active therapeutic components of CBT-I. Each module was unlocked weekly, and participants will have access to the intervention for 12 weeks. The general sleep knowledge session was purposively added in this sleep related RCT to meet the expectation of the participants. Individualized text messages will be sent to the participants regularly to remind them of completing the sessions and sleep diaries on time. The participants will also be contacted weekly to prevent possible dropout from occurring during the intervention.

Assessments

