Assessments will be delivered at baseline, post-treatment, 6-month follow-up and 12month follow-up. At baseline, all participants will be interviewed for their basic demographic and clinical characteristics (age, sex, education, height, weight, current medications etc). Self-administered questionnaires will be completed online to assess depressive symptoms and severity (PHQ-9), anxiety (Generalised Anxiety Disorder 7item, GAD-7⁶⁰), suicidal ideation (Beck Scale for Suicide Ideation, BSSI⁶¹), sleep symptoms (ISI, 7-Day Daily Sleep Diary), daytime symptoms (Multidimensional Fatigue Inventory, MFI⁶²), chronotype (reduced Morningness-Eveningness Questionnaire, rMEQ ⁶³), sleep-related thoughts and behaviors (brief version of dysfunctional beliefs and attitudes about sleep, DBAS-16⁶⁴), circadian rhythms and sleep parameters (7-Day Daily Sleep Diary). During the intervention, participants will additionally complete ongoing assessments to evaluate their sleep symptoms, mood symptoms and sleep parameters (ISI, PHQ-9, GAD-7, 7-Day Daily Sleep Diary) at post-session 2 and post-session 4. Saliva collection kit will be mailed to participants at baseline to collect their salivary cortisol and DNA, and at 12-month follow-up to collect their salivary DNA. After finishing the intervention, each participant will be paid CNY100 (or HKD equivalent) for his or her participation. Part of the participants in e-CBT-I group will be invited to receive semi-structural individual interviews about user experience and satisfaction towards e-CBT-I intervention via phone after intervention, and will be additionally paid CNY100 (or HKD equivalent) for his or her participation.

At post-treatment, 6-month follow-up and 12-month follow-up, participants will receive phone calls from the independent researcher blinded to the randomization status for diagnostic interviews to examine whether they have current insomnia measured by ICD-10 Classification of Mental and Behavioral Disorders, MDD or suicidality measured by MINI. Part of the diagnostic interviews will be audiotaped and second-rated by an independent rater to assess interrater reliability after obtaining participants' consents. In addition, participants will complete online questionnaires similar to those at baseline. After finishing the 12-month follow-up, each participant will be paid CNY50 (or HKD equivalent) for his or her participation.

Outcomes

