The primary outcomes include remission rate of insomnia disorder conformed by ICD-10 Classification of Mental and Behavioral Disorders, change of insomnia symptoms measured by ISI, occurrence of MDD conformed by MINI and change of depressive symptoms measured by PHQ-9. Secondary outcomes include incidence of suicidality which includes plans and attempts as measured by MINI and change of anxiety symptoms measured by GAD-7. Other pre-specified outcome include incidence of suicidal ideation measured by BSSI, change of daytime symptoms measured by MFI, change of sleep-related thoughts and behaviors measured by DBAS-16, change of circadian rhythms measured by 7-Day Daily Sleep Diary and MEQ, and change of sleep parameters including time in bed (TIB), total sleep time (TST), sleep onset latency (SOL), wake after sleep onset (WASO), sleep efficiency (SE) measured by 7-Day Daily Sleep Diary.

Sample Size Estimation

The sample size calculation was based on the occurrence of diagnosed depressive disorder because the primary aim of the current study was to prevent clinical depression. According to the previous meta-analysis, the incidence rate of depression is approximately 11% in the individuals with insomnia ¹⁵. As the study sample included a mixture of individuals without prior depression and those with a history of MDD, an expected 50% increase in the cumulative one-year occurrence of diagnosed depressive disorder is anticipated (16.5%). Based on the previous research on CBT-I and our trial data on sleep-focused treatment for depression, a 50% reduction of occurrence rate is expected for the intervention group. Power analysis using Stata suggested that a total of 282 participants per condition would be required to achieve a power of 0.80 whilst allowing a type I error of 0.05 detect a hazard ratio of 0.5 under 1:1 randomization. In view of the attrition rate from previous study (40%), a total of 940 participants would be required (470 participants in each group x 2 groups). A protocol amendment was submitted to reduce the sample size to 708 (354 per group) based on an estimated attrition rate of approximately 20%, as it was determined that the attrition rate was lower than initially expected.

Data Analysis

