All main analyses will be based on the intent-to-treat (ITT) approach. We aim to obtain full follow-up data on every participant, but missing data may be inevitably expected due to withdrawal, loss-to-follow-up, or non-response questionnaire items. Baseline characteristics will be presented as percentage for categorical variables and as means (standard deviations) for continuous variables. The primary and secondary outcomes with continuous variables will be examined by using linear mixed-effects model (LMM) analysis. The changes of efficacy indicators (e.g., PHQ-9) from baseline to each follow-up time points and intervention differences were tested by the MIXED module of Stata, with major measures at each time point nested within each participant. Interaction effects of group by time will be examined to compare the effects of treatment on the major outcomes. Between-group difference in the estimated mean change from baseline to each time points from mixed models and Cohen's d will be used to calculate effect sizes. Current MDD will be analyzed by the survival analysis and the Mentel-Cog log rank test. An observation will be right censored to the day after the last point of interview when a participant is no longer eligible to experience a depressive episode, e.g., lost to follow-up or completed the trial without experiencing a depressive episode (12month follow-up after intervention). The effect of the intervention on insomnia remission will be analyzed using generalized estimating equations (GEE). The GEE analysis will be conducted by using the XTGEE module of Stata. Mediation analysis using maximum likelihood estimation within a structural equation modeling framework will be used to determine which outcomes are mediated by changes in candidate factors including sleep symptoms, mood symptoms, sleep-related unhelpful thoughts and maladaptive behaviors, circadian rhythm disruption and sleep parameters at follow-up. Sensitivity analyses will be conducted using imputation methods to examine the robustness of the results based on

different assumptions about the missing data. Strata variables (sex and insomnia severity) at baseline will be included as covariates in all analyses. Variables with a p value ≤ 0.05 will be considered statistically significant.

Ethics & Other Considerations

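### MDD sizes the trial at HR 0.5 but is seen only at three interviews: its primary analysis should be a named, covariate-adjusted model by interview interval, including baseline PHQ-9, that reports the HR with 95% CI

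*Combined protocol and SAP*

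**What the plan says.** - **Sizing** (Sample Size Estimation). The calculation rests on diagnosed depressive disorder, with 16.5% expected in controls over one year. The aim is to "detect a hazard ratio of 0.5 under 1:1 randomization", which gives 282 per arm, or 354 after allowing for about 20% attrition.
- **Ascertainment** (Assessments). "At post-treatment, 6-month follow-up and 12-month follow-up, participants will receive phone calls from the independent researcher blinded to the randomization status" for MINI interviews. PHQ-9 is collected from everyone at baseline.
- **Analysis** (Data Analysis). "Current MDD will be analyzed by the survival analysis and the Mentel-Cog log rank test". The date rule given for participants without an event is this: "An observation will be right censored to the day after the last point of interview" for those lost, or who "completed the trial without experiencing a depressive episode (12month follow-up after intervention". Also: "Strata variables (sex and insomnia severity) at baseline will be included as covariates in all analyses". The continuous outcomes get a named mixed model and insomnia remission gets GEE; MDD gets no named model. The effect-size sentence covers only mean changes and Cohen's d.
- **Course length** (Intervention). e-CBT-I access lasts 12 weeks, "allowing them additional time to complete the intervention in case they were unable to completed it within the initial 6-week period". For health education, "Each module was unlocked weekly, and participants will have access to the intervention for 12 weeks". Both arms get text reminders and weekly contact.
- **Pointers to origin and event.** Hypothesis 1 in Study Design counts depressive onsets at post-intervention as well as at 6 and 12 months. Data Analysis adopts intention to treat. Ethics & Other Considerations takes participants out of the study once MDD is diagnosed at an assessment.

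**The concern.** Three things do not fit together for the outcome that sizes the trial.

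1. Sex and insomnia severity must enter all analyses. An ordinary log-rank test takes no covariates, so the rule cannot be applied to MDD until a model or a stratified test is named.
2. The trial is powered on a hazard ratio, but no hazard ratio or confidence interval is planned.
3. MDD status is learnt only at three interviews, so onset is interval-censored. On a day scale, event and censoring times would reflect when people were interviewed, and the interviews follow a course that may take 6 to 12 weeks.

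At stake are the pre-specification of the model and estimate for this outcome, a little power from a baseline measure already in hand, and robustness if interview timing differs between arms.

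**Working it through.** **1. Reproduce the sizing.** Freedman's log-rank formula, two-sided 0.05, power 0.80, HR 0.5:
- Events = (1.960 + 0.842)² × (1.5/0.5)² = 70.64, using unrounded normal quantiles.
- Intervention risk under proportional hazards = 1 − 0.835^0.5 = 0.0862.
- Per arm = 70.64 / (0.165 + 0.0862) = 281.2, so 282, as stated.
- Attrition: 282/0.6 = 470, as stated; 282/0.8 = 352.5, so 353 against the stated 354, a rounding-level difference.

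**2. What the unplanned estimate would look like.** Expected events are 282 × 0.165 = 46.5 and 282 × 0.0862 = 24.3. SE(log HR) = √(1/46.5 + 1/24.3) = 0.250. The 95% CI around 0.5 is 0.5 × exp(±1.96 × 0.250) = 0.31 to 0.82. This is the trial's precision, not harm done by the omission.

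**3. Origin.** Assume a constant hazard and completion at 1.5 to 3 months, with follow-up to 12 months after treatment. The share of events at or before the post-treatment interview is then 1.5/13.5 = 11% to 3/15 = 20%. A clock starting at the end of the intervention would put these at time zero or drop them, although Hypothesis 1 counts them.

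**4. Does the rule matter with equal timing?** In 400 simulated trials at true HR 0.5, the mean HR stayed between 0.50 and 0.51 across the event-date, tie and origin rules tried.

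**5. Simulation by test.** The documents supply the 16.5%, the 354 per arm, the 20% attrition and the 6-to-12-week window. The rest is assumed:
- dropout spread evenly over the three interviews, and a constant hazard;
- PHQ-9 HR 1.3 per SD;
- completion either uniform over days 42 to 84 or skewed early within that window;
- interviews at completion, +182 and +365 days, plus a lag of up to 7, 14 or 28 days;
- events dated to the interview, and censoring the day after the last one.

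One arm's completion is shifted by 0 to 14 days. Type I error at nominal 0.05, with 1,500 runs per setting:

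| Shift between arms | Day-scale log-rank from randomisation |
|---|---|
| 0 days | 0.041–0.060 |
| 3 days | 0.057–0.086 |
| 7 days | 0.124–0.212 |
| 14 days | 0.251–0.501 |

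Across all these settings the complementary log-log interval model gave 0.041–0.063, and the stratified log-rank on interview number 0.043–0.061. The mechanism is that the earlier arm's events at an interview are compared with a risk set holding both arms. Many of the later arm's final-interview events fall after the earlier arm has been censored.

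The inflation depends on the assumed spread: completion uniform over days 42 to 56 gives 0.20 to 0.52 at 7 days. Counting days from completion gives 0.045 to 0.062.

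**6. Power at HR 0.5** (lag up to 14 days, 2,000 runs; uniform, then early-skewed completion):

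| Timing | Day-scale log-rank from randomisation | Interval model |
|---|---|---|
| Equal | 0.829, 0.837 | 0.837, 0.844 |
| Control 7 days later | 0.578, 0.504 | 0.860, 0.871 |
| e-CBT-I 7 days later | 0.953, 0.965 | 0.806, 0.812 |

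**7. Baseline PHQ-9.** Adjusted minus unadjusted interval-model power (6,000 paired runs, equal timing) is 0.0, 0.2, 1.0 and 2.9 points at an assumed HR per SD of 1.0, 1.3, 1.6 and 2.0.

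**The case against.** The strongest reply is that this is mostly missing detail that the documents largely settle. Hypothesis 1 and intention to treat point to randomisation as origin. The phrase about 12 months after the intervention says when follow-up ends, not when it starts. Outcome assessment at blinded interviews, with removal on diagnosis, points to the first positive interview as the event. The log-rank test could be meant as stratified, which would use both stratification variables. With equal timing, neither the HR nor the power moves materially.

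All of that stands, and it removes two readings. A reader might infer that the time origin is wide open, with the end of intervention as natural as randomisation; the text favours randomisation. A reader might also infer that the planned test is known to be anti-conservative. The documents do not support this. The inflation needs interviews tied to each person's completion, arms that finish at different times, a day scale, and a clock from randomisation. Both arms have the same weekly unlocking, 12-week access, reminders and contact, and interviewers are blinded.

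What the reply does not answer is that no model or HR is stated, that even a stratified log-rank would give no HR, and that a collected prognostic measure lies outside the stated covariates.

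**Conclusion.** The point holds as a worthwhile improvement to the analysis plan, not as an error in the design. The sample size is sound. With equal interview timing the gain from changing the test is about one power point or less (0.829 to 0.837; 0.837 to 0.844), and PHQ-9 adjustment adds 0 to 3 points over an assumed HR per SD of 1.0 to 2.0. The further benefit is protection: if one arm finished about 7 days later with completion spread over days 42 to 84, a day-scale log-rank from randomisation would have type I error of about 0.12 to 0.21, while the interval model stays near 0.05. That difference in timing is assumed.

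A reader might infer that an interval model makes timing irrelevant. It does not. If one arm is interviewed later, its first interval is longer: the simulated median null HR is 1.01 to 1.02 at 7 days and 1.03 to 1.05 at 14 days, and power shifts as shown above.

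**What to change.** In Data Analysis, for MDD:

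- Make the primary analysis a survival model by interview interval, with treatment, interval, sex, insomnia severity and baseline PHQ-9 (continuous). A discrete-time complementary log-log model is suitable, as is a grouped-time Cox model with proper tie handling. Ties matter slightly: at true HR 0.5, an unadjusted Cox model with Breslow ties gave a median of 0.509, against 0.498 for complementary log-log.
- Report the HR with 95% CI.
- State randomisation as the origin, and the interview at which MDD is first diagnosed as the event.
- Keep the log-rank test as support, run on interview number and stratified by sex and insomnia severity.
- Report interview dates by arm, so that any difference in interval length is visible.

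The cost is plan wording and a few lines of Stata. No new data are needed, and 282 and 354 per arm are unchanged. The downside is the small drift in the null HR described above.

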To address the limitations in the existing literature, we propose to conduct a RCT of targeted prevention intervention to validate the treatment effect of e-CBT-I on insomnia disorder and examine whether digitally delivered insomnia treatment can reduce the risk of depression in a high-risk group of youth population. To further explore the mechanisms underlying the association between insomnia treatment and depression, we will evaluate whether changes in candidate factors including insomnia symptoms, mood symptoms, sleep-related unhelpful thoughts and maladaptive behaviours, and circadian rhythm disruption will mediate the changes in depressive symptoms. On a conceptual level, the proposed interventional study will also allow us to further test the causal pathway between sleep disturbance and major depression, by intervening and treating insomnia as a preventive measure of depression. On a pragmatic level, digital approach to insomnia intervention for prevention of youth depression, if effective, may have important public health implications given its high accessibility to the young populations.

Methodology

Study Design

A randomized, assessor-blind, parallel group-controlled trial will be conducted in youth with insomnia and subclinical depression. All qualified participants will be randomly assigned via online system to receive e-CBT-I or health education (HE). Randomization will be stratified by sex and the severity of insomnia. Assessments will be carried out at baseline, post-treatment, 6-month follow-up and 12-month follow-up. Additional assessments will be given upon the completion of sessions 2 (post-session 2) and 4 (post-session 4) to evaluate sleep symptoms, mood symptoms, circadian rhythms and sleep parameters of participants. Saliva collection kit will be mailed to participants at baseline to collect their salivary cortisol and DNA, and at 12-month follow-up to collect their salivary DNA. Semi-structural individual interviews about user experience and satisfaction towards e-CBT-I intervention via phone calls will be given to part of the participants in e-CBT-I group after intervention.

Main hypothesis in the present study include:

1. Youth receiving e-CBT-I will have fewer onsets of depressive disorder and higher rates of remission in insomnia disorder at post-intervention, 6-month and 12-month compared

to those in control group.

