Youth in e-CBT-I group will have fewer insomnia symptoms, depressive symptoms, suicidal ideation, plans and attempts than those in control group at each timepoint.
 Changes in candidate factors including insomnia symptoms, mood symptoms, circadian rhythms and sleep parameters will mediate the outcomes.

Recruitment and Screening

Potential participants will be recruited from colleges and senior secondary school in Hong Kong and mainland China and will be identified from various sources. These will include the local partner schools in Hong Kong established from our previous research projects. Partner schools in mainland China will be recruited by our collaborators with the school links in mainland China. Through our partner schools, students will be introduced to this study, and they will be asked to return the signed informed consents and leave their contact (e.g., email) in the reply slip to the research team if they are interested in taking part in the study. Furthermore, potential participants will be recruited through community referrals and advertising via social media and emails in Hong Kong and mainland China. Interested participants will be asked to complete the screening assessments, including Patient Health Questionnaire-9 (PHQ-9)⁵⁵ and Insomnia Severity Index (ISI)⁵⁶ via an online portal (Qualtrics). Participants who have an ISI score of no less than 15 and a PHQ-9 score between 4 and 20 will be further invited for diagnostic interview through telephone to screen for insomnia (International Statistical Classification of Diseases and Related Health Problems10th Revision Classification of Mental and Behavioral Disorders, ICD-10 Classification of Mental and Behavioral Disorders ⁵⁷), MDD and suicidality including ideation, plans and attempts (Mini International Neuropsychiatric Interview, MINI ⁵⁸). A potential participant who meets the inclusion criteria (see below) will be eligible to take part in the study.

Participants

Inclusion criteria and exclusion criteria for participants are as follows:

Inclusion criteria

- 1. Native Han youth in Hong Kong and mainland China, aged between15-25
- 2. A diagnosis of insomnia disorder measured by ICD-10 Classification of Mental and Behavioral Disorders
- 3. The presence of moderate or severe insomnia measured by a score of 15 or above on ISI
- 4. The presence of subclinical depression assessed by a score of more than 4 but less than 20 on PHQ-9
- 5. Access to smartphones

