- 6. Ability to read and understand research protocol

Exclusion criteria

- 1. Shift workers
- 2. The presence of prominent suicidality (suicide plans and suicide attempts) measured by MINI via telephone interview
- 3. A clinical diagnosis of psychosis, schizophrenia, bipolar disorder, or neurodevelopmental disorders

- 4. Current medical conditions that could cause poor sleep quality and sleep continuity disruption, such as eczema
- 5. The presence of current MDD or a prior episode of MDD within past two months measured by MINI via telephone interview
- 6. Women during pregnancy or lactation
- 7. Currently receiving psychological treatment for insomnia provided by a psychologist and/or pharmacological treatment for depression

Intervention

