All participants will provide their online informed consent before participation. Potential adverse effects will be evaluated by self-reporting of existing adverse effects for frequency and severity ⁶⁵. Participants will be excluded from the study and provided with information for further treatment if they are diagnosed with MDD or show a suicidal risk upon assessments. The proposed study will be conducted in compliance with the protocol, the ICH-CGP Guideline, and all other applicable regulatory requirements. The ICH shall include the elements required by the International Conference on Harmonization (ICH) Good Clinical Practice (GCP) Guideline and local regulation requirements, and will adhere to the ethical principles based on the Declaration of Helsinki.

References:

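### The rule excluding participants with MDD or suicidal risk is not limited to screening; applied after randomisation, it would make later outcome data missing because of an outcome

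*Combined protocol and SAP*

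**What the plan says.** The rule stands under Ethics & Other Considerations: "Participants will be excluded from the study and provided with information for further treatment if they are diagnosed with MDD", continuing "or show a suicidal risk upon assessments". It gives no time point and does not say whether being excluded ends the intervention, data collection, or both.

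Other sections bear on how to read it:

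- **Recruitment and Screening** uses the same vocabulary before enrolment: "Interested participants will be asked to complete the screening assessments". The telephone interview at that stage covers "MDD and suicidality including ideation, plans and attempts".
- **Exclusion criteria** already bar both conditions at entry. Criterion 2 reads "The presence of prominent suicidality (suicide plans and suicide attempts) measured by MINI via telephone interview" and criterion 5 reads "The presence of current MDD or a prior episode of MDD within past two months measured by MINI via telephone interview".
- **Study Design** and **Assessments** use the word for the scheduled visits: "Assessments will be carried out at baseline, post-treatment, 6-month follow-up and 12-month follow-up" and "Assessments will be delivered at baseline, post-treatment, 6-month follow-up and 12month follow-up". The Assessments section repeats the MINI interview for MDD and suicidality at all three post-baseline visits and exempts nobody.
- **Outcomes** makes MDD occurrence, ISI change, PHQ-9 change and insomnia remission primary. Suicidality (plans and attempts by MINI) is secondary.
- **Data Analysis** specifies intention to treat and aims for complete follow-up of all participants. It expects missing data from withdrawal, losses to follow-up and unanswered items, and does not name removal by rule. Imputation sensitivity analyses are planned, but their assumptions are not specified.

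**The concern.** Both triggers are trial outcomes. If a positive interview after randomisation took a participant out of the study and ended data collection, everything scheduled afterwards would be missing because of that outcome. This would affect three of the four primary outcomes (ISI, PHQ-9, insomnia remission) and later suicidality data. It would be in tension with the visit schedule and with the follow-up aim in Data Analysis.

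The time-to-MDD analysis is touched in one way only. Removal after an MDD diagnosis does no harm there, because the event has already been counted. Removal for suicidal risk before any MDD would be censoring that is potentially informative, since those participants may differ in their later risk of MDD. The censoring examples in Data Analysis do not mention this case.

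The term suicidal risk is also not tied to exclusion criterion 2. That criterion names plans and attempts, whereas the recruitment interview also covers ideation.

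**Working it through.** **Two readings side by side.** *Screening only:* Recruitment and Screening speaks of participants and screening assessments before enrolment. The two triggers mirror exclusion criteria 2 and 5. The rule adds referral information that the criteria lack, so it need not be redundant. *Also after randomisation:* the criteria already deal with entry. Study Design and Assessments use the word assessments for the baseline and follow-up visits, and the interview that would detect either trigger is repeated at each later visit. No section settles the choice.

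**Inputs (Sample Size Estimation).** One-year control occurrence 16.5%; 50% reduction, also expressed as a hazard ratio of 0.5; power 0.80; type I error 0.05 (taken as two-sided); 282 per arm, raised to 354 per arm for about 20% attrition.

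**Reproducing the plan's figure.**

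- Freedman log-rank events: (1.960 + 0.842)² × (1.5/0.5)² = 70.6, rounded up to 71.
- e-CBT-I risk under a hazard ratio of 0.5: 1 − 0.835^0.5 = 0.0862.
- Mean risk: (0.165 + 0.0862)/2 = 0.1256. Total 71/0.1256 ≈ 565, or about 282.6 per arm, which agrees with 282.
- Attrition: 282/0.6 = 470; 282/0.8 = 352.5, against a stated 354.

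The sample size is not in dispute.

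**How many would meet the MDD trigger** (354 per arm, no other dropout).

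- Control: 354 × 0.165 = 58.4.
- e-CBT-I: 354 × 0.0825 = 29.2 (halved rate) to 354 × 0.0862 = 30.5 (halved hazard).
- Ratio of control to e-CBT-I: 1.9 to 2.0.

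**How many would lack 12-month data.** Only cases found before the 12-month interview lose later data. The documents give no timing, so the share is assumed.

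| Share found before 12 months | Control | e-CBT-I | Gap (percentage points) |
|---|---|---|---|
| 25% | 14.6 (4.1%) | 7.3–7.6 (2.1–2.2%) | 2.0–2.1 |
| 50% (even onset over the year) | 29.2 (8.3%) | 14.6–15.3 (4.1–4.3%) | 3.9–4.1 |
| 75% | 43.8 (12.4%) | 21.9–22.9 (6.2–6.5%) | 5.9–6.2 |

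If only the 80% expected to be followed can be diagnosed (354 × 0.8 = 283.2 per arm), 46.7 control and 23.4–24.4 e-CBT-I participants would meet the trigger. Half of them is 23.4 and 11.7–12.2. The plan does not say whether its 20% attrition already includes such removals, so the two are not combined.

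**How many assessments would be lost.** Assume even onset, with post-treatment falling 6 to 12 weeks into the year (the Intervention section gives a 6-week course with 12 weeks of access).

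- Found at post-treatment, two later visits lost: 6/52 = 12% to 12/52 = 23%.
- Found at 6 months, one later visit lost: 50% − 12% = 38% down to 50% − 23% = 27%.
- Visits lost per case: 0.5 + 0.115 = 0.615 to 0.5 + 0.231 = 0.731.
- Cases in both arms: 58.4 + 29.2 = 87.6 to 58.4 + 30.5 = 88.9.
- Lost: 87.6 × 0.615 = 54 to 88.9 × 0.731 = 65, of 708 × 3 = 2,124 scheduled post-baseline assessments, or 2.5–3.1%.

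Removals for suicidal risk would add to these counts. The documents give no rate for them.

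**The case against.** The harm needs two things that the text does not state: that the rule operates after randomisation, and that it ends data collection. Assessments and Data Analysis point against the second, because they schedule every later visit without exemption and aim for complete follow-up. The wording echoes the exclusion criteria, while Data Analysis uses other terms for departures during the trial. Plans and attempts are a natural reading of suicidal risk, given criterion 2 and the suicidality outcome. The censoring list is given as examples, so it is open. All of this stands as a reason for caution. It does not remove the ambiguity, because the rule refers to assessments without restricting them to screening.

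The planned models also offer some protection. The trigger is a recorded MINI result, and PHQ-9 and ISI are collected at the same visits, so the mixed model may partly handle missingness that depends on those scores. Unweighted GEE for insomnia remission is more exposed, since it generally requires data missing completely at random. If everyone diagnosed with MDD left, any model would be extrapolating for them.

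The counts may also be high. The interview looks for current MDD, so an episode that resolves between visits might never trigger the rule, whereas the 16.5% is cumulative.

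A reader might go further and infer a loss of about 6% of assessments. That figure (66.7 cases × 2 = 133 of 2,124) needs 75% of the year's cases to be found at post-treatment, which nothing in the documents supports.

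**Conclusion.** The point holds as a conditional one and should be fixed. The rule is not limited to screening. Followed literally after randomisation with data collection ended, it would make later primary and secondary data missing because of an outcome, in tension with Assessments and Data Analysis.

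At the plan's rates, with even onset and no other dropout, about 29 control (8%) and 15 e-CBT-I (4%) participants would lack 12-month data, and about 3% of scheduled assessments would be lost. The difference between arms follows from the assumed treatment effect and would not be expected under the null.

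A reader might also infer one of the following, none of which the documents support:

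- *That randomised participants were in fact removed.* The documents do not say so.
- *That the intention-to-treat set is broken.* The rule does not say that anyone is dropped from the analysis.
- *That the primary MDD analysis or its 282 per arm is undermined by removal after MDD.* It is not; only removal for suicidal risk before MDD could matter there.
- *That the PHQ-9 or remission results are biased in a known direction.* Neither direction nor size can be determined.

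**What to change.** Reconcile Recruitment and Screening, Exclusion criteria, Assessments, Data Analysis, and Ethics & Other Considerations:

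1. State whether the rule applies at screening only or also after randomisation, and how suicidal risk relates to exclusion criterion 2. No threshold, care or treatment rule is proposed here. If screening only was meant, one clause settles the timing.
2. For randomised participants, state that the outcome assessments already scheduled continue to be requested unless consent is withdrawn, that the data are analysed as randomised, and that any removals are reported by arm and reason. This concerns data collection, not clinical management.
3. If removals have already occurred, cover them with one scenario in the imputation sensitivity analyses already planned, for example a delta-adjusted one. No data after removal would be available to inform the model for these participants.

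The cost is a few sentences of text and minor extra analysis. There are no new visits and no change in sample size: the roughly 54–65 assessments at issue in the illustration are already on the schedule.
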